6.4.7. Subgroup Analysis

Analysis of efficacy and safety will also be performed for subgroups of interest including:

Table 3: Subgroups for Analysis

Number	Subgroup	Categories and comments			
1	Gender	Male	Female		
2	Age #1	< 65 vs ≥ 65 years			
3	Age #2	< 75 vs ≥ 75 years			
4	Body mass index #1	≤ vs > median			
5	Body mass index #2	Quartiles			
6	Race	White	Black	Other	
7	Baseline statin use	Yes	No		
8	Baseline statin intensity	High intensity	Not high intensity		
9	Other lipid management therapy	Any statin with other lipid management therapy	No statin but other lipid management therapy	No lipid management therapy	
10	Baseline triglyceride level #1	<200 mg/dL vs ≥200 mg/dL			
11	Baseline triglyceride level #2	≤ vs > median			
12	Metabolic disease [1]	Diabetes	Metabolic syndrome without diabetes	Neither	
13	ASCVD status	ASCVD	ASCVD risk equivalents		
14	Renal impairment by eGFR categories - mL/min/1.73m ² [2]	≥15 to <30	≥30 to <60	≥60 to <90	≥90
15	History of allergy [3]	Yes	No		
16	Baseline LDL-C #1	≤ vs > median			
17	Baseline LDL-C #2	Quartiles			
18	Study center region	North America	Europe	South Africa	
19	Post baseline LDL-C [4]	≤25 at any time point vs >25 mg/dL at all time points			

[1] Metabolic syndrome is not based on medical history but will be defined according to the American Heart Association (AHA) definition (see [Reference 1](#)).

[2] Creatinine clearance (CrCl) values using the Cockcroft and Gault estimation:
CrCl = $\{((140 - \text{age}) \times \text{weight}) / (72 \times \text{Serum Creatinine})\} \times 0.85$ (if female)

[3] A history of allergy was identified using the following high-level group term (HLGT): allergic conditions.

[4] For descriptive summary of PCSK9 data only.

Baseline variables to be analyzed by subgroup:

Disposition
Protocol Deviations
Demographics and Baseline Characteristics
Targeted Medical History
Other Medical History
Medical History of Partial or Complete Statin Intolerance
Study Drug Administration
Day 1 Concomitant Medications
New or Changed Concomitant Medications

Prior Medications
Prior Lipid Modifying Therapies
Day 1 Lipid Modifying Therapy Usage
New or Changed Lipid Modifying Therapy Usage
Shift from Baseline in Statin Intensity

Safety variables to be analyzed by subgroup:

Treatment Emergent Adverse Events
Treatment Emergent Serious Adverse Events
Treatment Emergent Adverse Events at the Injection Site
Withdrawals due to TEAEs

Efficacy variables to be analyzed by subgroup:

Co-Primary #1: Percentage change in LDL-C from baseline to Day 510 – ANCOVA – Washout Imputation
Co-Primary #2: Time adjusted percentage change in LDL-C from baseline after Day 90 and up to Day 540. This is the average percentage change in LDL-C from baseline over the period after Day 90 and up to Day 540 – MMRM – control-based PMM
Key Secondary #1: Absolute change in LDL-C from baseline to Day 510 – MMRM – control-based PMM
Key Secondary #2: Time adjusted absolute change in LDL-C from baseline after Day 90 and up to Day 540 – MMRM – control-based PMM
Key Secondary #3: Percentage change from baseline to Day 510 in PCSK9, total cholesterol, ApoB, and non-HDL-C – MMRM – control-based PMM
Other Secondary #3: Actual value, absolute change and percentage change in LDL-C from baseline to each assessment time up to Day 540 – Descriptive Stats
Other Secondary #6: Actual value, absolute change and percentage change in other lipids, lipoproteins, apolipoproteins, and PCSK9 from baseline at each subsequent visit to Day 540 – MMRM
Other Secondary #6: Actual value, absolute change and percentage change in other lipids, lipoproteins, apolipoproteins, and PCSK9 from baseline at each subsequent visit to Day 540 – Descriptive Stats*

* Post baseline LDL-C subgroup included for PCSK9 summary table only.

6.4.8. Safety Analysis

The safety objectives of this study are to evaluate the safety and tolerability profile of inclisiran.

6.4.8.1. Adverse Events

The Medical Dictionary for Regulatory Activities (MedDRA) dictionary (v20.1) will be used for coding AEs. An AE (classified as preferred term) occurring during the treatment period will be counted as a treatment emergent AE (TEAE) either if it is not present at Day 1 before treatment or if it is present before treatment but increased in severity during the treatment period.

The following summary tables will be presented:

- Overall Summary of TEAEs
- TEAEs by SOC and PT
- TEAEs by PT
- Common (2% within either treatment group) by PT
- TEAEs by SOC, PT, and Severity

- TEAEs by SOC, PT, and Relationship to Study Drug
- Related TEAEs by SOC, PT, and Severity
- Treatment Emergent Serious AEs (TESAEs) by SOC and PT
- TESAEs by PT
- TESAEs by SOC, PT, and Severity
- TESAEs by SOC, PT, and Relationship to Study Drug
- Related TESAEs by SOC, PT, and Severity
- TEAEs Leading to Withdrawal of Study Treatment by SOC and PT
- TEAEs with a Fatal Outcome by SOC and PT

If more than one event occurred with the same preferred term for the same subject, the subject will be counted only once for that preferred term using the most severe or related occurrence for the summary by severity, or relationship to study drug, respectively.

For common (2% within either treatment group) TEAEs, serious TEAEs and TEAEs leading to withdrawal of study medication, risk ratios along with 95% confidence intervals will be presented to compare treatment groups with respect to risk.

The following additional adverse events (Refer to [Appendix 5](#), Additional Adverse Events Investigations) will also be assessed:

1. Adverse Events at the Injection Site
2. Hepatic events
3. Renal events
4. Hypersensitivity
5. Neurological events and Neurocognitive disorders
6. Ophthalmological events

Clinically relevant TEAEs at the injection site will also be tabulated. See [Appendix 6](#) for a list of clinically relevant injection site preferred terms.

The time to the first TEAE at the injection site will also be summarized. Only subjects with a TEAE at the injection site will be included in the analysis. The time (hours) will be calculated from the date of the most recent administration of study drug. The duration of the TEAE will also be summarized. The same analyses will be performed for each individual TEAE PT at the injection site. The time to the first clinically relevant adverse event at the injection site will be analyzed similarly.

Any immune-related events will be identified in the SOC of immune system disorders.

Listings will be presented for subjects with SAEs/AEs leading to a discontinuation or death. Listings of SAEs and Death will also be provided.

6.4.8.2. Laboratory Tests

Laboratory values will be summarized by treatment group, including the observed value, changes and percent changes from baseline at each time point.

A shift analysis using the normal range (except for eGFR and HbA1c) will be done which counts the number of subjects with a low, normal or high value at baseline and a low, normal or high value post baseline.

The following ranges will be used for eGFR and HbA1c

- For eGFR, the categories will be Severe = <30 mL/min/1.73m²; Moderate = ≥ 30 to <60 mL/min/1.73m²; Mild = ≥ 60 to <90 mL/min/1.73m²; and Normal = ≥ 90 mL/min/1.73m².
- For HbA1c, the categories will be $\leq 5.6\%$, $\geq 5.7\%$ to $\leq 6.4\%$, and $\geq 6.5\%$.

The baseline and worst post-baseline value will be utilized for the shift tables. Note that the shift table dealing with the fasting glucose parameter will require the lab sample to be taken while fasting. Samples taken while the subject was not fasting will not be analyzed.

The number and percentage of subjects with potentially clinically significant (PCS) laboratory values and clinically significant (CS) laboratory values (refer to [Appendix 4](#) for the criteria) will be summarized by treatment group. Hemoglobin A1c criteria is explicitly stated in Appendix 4. All other PCS and CS criteria are met when both of the following occur:

- Post-baseline values meet the thresholds listed in Appendix 4
- Baseline values or any prior post-baseline values do not meet the thresholds listed in Appendix 4

PCS chemistry laboratory values will also be classified as follows:

- Abnormal baseline:
 - Non HbA1c: >1 and $\leq 3x$ ULN at baseline and >1 and $\leq 3x$ ULN at final visit
 - HbA1c: $\geq 6.5\%$ at baseline and $\geq 6.5\%$ and $\geq 0.5\%$ change from baseline at final visit
- Elevated further:
 - Non HbA1c: >1 and $\leq 3x$ ULN at baseline or post baseline and becoming $> 3x$ ULN post baseline
- Final visit:
 - Non HbA1c: >1 and $\leq 3x$ ULN at final visit only but not at baseline or previous visits
 - HbA1c: $\geq 6.5\%$ and $\geq 0.5\%$ change from baseline at final visit only but not at baseline or previous visits
- Persistently elevated:
 - Non HbA1c: >1 and $\leq 3x$ ULN at a post baseline visit and remains >1 and $\leq 3x$ ULN until final visit
 - HbA1c: $\geq 6.5\%$ and $\geq 0.5\%$ change from baseline at a post baseline visit and remains $\geq 6.5\%$ and $\geq 0.5\%$ change from baseline until final visit
- Resolved:

- Non HbA1c: >1 and ≤ 3 x ULN at baseline or post baseline, resolved to $<$ ULN at any post baseline visit, and remaining $<$ ULN at final visit
- HbA1c: $\geq 6.5\%$ at baseline or $\geq 6.5\%$ and $\geq 0.5\%$ change from baseline for post-baseline, resolved to $<6.5\%$ and $<0.5\%$ change from baseline at any post baseline visit, and remaining $<6.5\%$ and $<0.5\%$ change from baseline at final visit

Separate listings of all subjects with PCS and CS laboratory values will be presented. Subjects will appear once per lab parameter but may appear under multiple lab parameters. The worst post-baseline value will be utilized in the analyses.

The number and percentage of subjects satisfying Hy's Law will also be tabulated by treatment group based on the following lab findings:

- Any elevated post-baseline aminotransferases defined as:
 - ALT > 3 x ULN or
 - AST > 3 x ULN
- Elevated post-baseline serum total bilirubin (TBL) > 2 x ULN and serum alkaline phosphatase (ALP) levels < 2 x ULN

Subjects must meet all of the criteria listed above at the same time point and have normal lab parameters (ALT, AST, TBL) at baseline to be considered a Hy's Law case.

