#### 10.4.4.2. Laboratory Tests

Laboratory values will be summarized by treatment group, including changes and percent changes from baseline at each time point. Analyses will also be performed for each laboratory parameter by treatment group for incidence rates of both potentially clinical significant (PCS)/clinically significant (CS) values for subjects without PCS/CS value at baseline.

Numerical values of laboratory parameters from different local laboratories with different units and normal ranges will be converted to the conventional units and normalized to a standard set of reference/normal ranges. The normalization process will be performed and separated by each of the laboratory parameters. A shift analysis by normal range will be done which counts the number of patients with a low, normal or high value at baseline and a low, normal or high value post baseline.

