6.3. General Statistical Considerations and Definitions

6.3.1. General Statistical Methods

All study-collected data will be summarized by treatment group using descriptive statistics, graphs, and/or raw data listings. Categorical variables will be summarized using counts and percentages. Percentages are based on the number of subjects in the analysis set for whom there are non-missing data, unless otherwise specified. Continuous variables, including changes from Day 1, will be summarized using descriptive statistics (n, mean, standard deviation [SD], median and interquartile range [first and third quartiles], minimum and maximum).

All p-values will be two-sided. All p-values will be rounded to three decimal places using the following algorithm. If the fourth digit of the p-value is less than or equal to 4, the p-value will be rounded down. If the fourth digit of the p-value is greater than or equal to 5, the p-value will be rounded up. All p-values rounded to 0.000 will be presented as '<0.001' and p-values that round to 1.000 will be presented as '1.000'.

Absolute change and percent change from baseline will be calculated as follows:

- Absolute Change = Value at Day X – Baseline value.
- Percent Change = (Absolute Change/Baseline value)*100%.

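### For laboratory rows that a subject can already meet at baseline, the SAP drops those subjects from the PCS/CS numerator but by default leaves them in the denominator, unlike the protocol

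*SAP*

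**What the plan says.** - **Statistic.** SAP 6.4.8.2 tabulates "The number and percentage of subjects with potentially clinically significant (PCS) laboratory values and clinically significant (CS) laboratory values" by treatment group, using the Appendix 4 thresholds. It states no denominator.
- **Numerator.** For every parameter except HbA1c, a post-baseline value must meet the threshold and a second condition must hold: "Baseline values or any prior post-baseline values do not meet the thresholds listed in Appendix 4". For HbA1c, "Hemoglobin A1c criteria is explicitly stated in Appendix 4"; that criterion does not exclude a raised baseline.
- **Default denominator.** SAP 6.3.1: "Percentages are based on the number of subjects in the analysis set for whom there are non-missing data, unless otherwise specified".
- **Protocol.** Section 10.4.4.2 plans "incidence rates of both potentially clinical significant (PCS)/clinically significant (CS) values for subjects without PCS/CS value at baseline", which is an at-risk set.
- **Declared changes.** SAP section 8 records that the identification of PCS/CS values was modified. It mentions no change of analysis set or denominator.
- **Hy's Law.** In the same SAP section, a case must "have normal lab parameters (ALT, AST, TBL) at baseline". Again no denominator is given. The protocol's laboratory analysis section plans no Hy's Law rate.

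**The concern.** The protocol applies the baseline restriction to the population. The SAP applies it to the case definition and leaves the population to a general default. A subject who already meets a threshold then counts towards the denominator of a rate to which, on the natural reading, that subject cannot contribute a case.

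At stake is the meaning of the absolute percentages in the liver, muscle and kidney laboratory tables. They would not be the incidence that the protocol planned, and without n/N a reader could not tell which denominator was used. Two programmers, one following protocol 10.4.4.2 and one following SAP 6.3.1, would print different tables.

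**Working it through.** The plan states no figure on this point, so there is none to reproduce.

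**Inputs**
- N = 750 per arm (SAP 6.2), taking all as treated with baseline and post-baseline values.
- q = share meeting the threshold at baseline. Not in the documents; assumed 1% to 30%.
- p = incidence among subjects not meeting it at baseline. Not in the documents; assumed 2% to 20%.
- The numerator rule is read as requiring that neither the baseline nor any earlier post-baseline value met the threshold.

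**Step 1: printed percentage**

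Cases = N(1 − q)p. With everyone in the denominator, the percentage is p(1 − q). With the at-risk denominator N(1 − q), it is p. The relative shortfall is q and the absolute shortfall is p × q.

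Example with q = 20%, p = 10%: 600 subjects are at risk and 60 become cases. 60/750 = 8.0%; 60/600 = 10.0%. The gap is 2 points (0.10 × 0.20).

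| q (assumed) | p = 2% prints as | p = 10% prints as | p = 20% prints as |
|---|---|---|---|
| 1% | 1.98% | 9.9% | 19.8% |
| 5% | 1.90% | 9.5% | 19.0% |
| 10% | 1.80% | 9.0% | 18.0% |
| 20% | 1.60% | 8.0% | 16.0% |
| 30% | 1.40% | 7.0% | 14.0% |

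**Step 2: which rows can have a material q**
- *ALT, AST and CK above 1 and up to 3 × ULN.* Exclusion criterion 7 removes liver enzymes on laboratory value only when they are unexplained, confirmed and above 3 × ULN. No entry criterion limits CK. These are the main rows affected.
- *ALT/AST above 3 × ULN and bilirubin above 2 × ULN.* The same criterion should leave q near zero. It acts at screening, whereas baseline is the last pre-dose value, so q need not be exactly zero.
- *HbA1c.* No baseline exclusion, so no mismatch.
- *Creatinine rise of at least 50%.* Cannot be met at baseline. The alternative limb of that row, above 2 mg/dL, can be.

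**Step 3: comparison between arms**

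With the same q in both arms, the factor (1 − q) cancels from the ratio. For p = 12% against 10% at q = 10%, the printed rates are 10.8% and 9.0%: the ratio stays 1.20 and the difference goes from 2.0 to 1.8 points.

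Chance imbalance in q has standard deviation √(2q(1 − q)/750), which is 0.0155 at q = 10% and 0.0207 at q = 20%. Multiplying by 1.96 and dividing by (1 − q) moves the ratio by about ±3.4% and ±5.1%. This variance combines with ordinary sampling variance; it does not add linearly to the margin. At p = q = 20%:
- all-subject difference, 95% half-width: 1.96 × √(2 × 0.16 × 0.84/750) = 3.71 points;
- with the at-risk number fixed at 600 per arm: 1.96 × √(2 × 600 × 0.2 × 0.8)/750 = 3.62 points.

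The net cost is about 0.1 point.

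**Step 4: Hy's Law**

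One case in 750 is 0.133%. If 10%, 20% or 30% of subjects lack normal baseline values, the at-risk figure is 1/675 = 0.148%, 1/600 = 0.167% or 1/525 = 0.190%. The count is the same either way.

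**The case against.** **The denominator is inferred.** Nothing in SAP 6.4.8.2 says that baseline-abnormal subjects are kept. The 6.3.1 rule gives way where something else is specified, the protocol does specify "for subjects without PCS/CS value at baseline", and section 8 declares no change to that. Using the protocol's set is therefore a possible reading. This stands as a limit on the claim: the denominator comes from a default, not an explicit rule. It does not remove the problem, because protocol section 10 leaves detailed specification to the SAP, and the SAP names an at-risk set where it wants one. The time-to-new-onset diabetes summary in 6.4.8.3.4, for example, is confined to subjects without diabetes at baseline.

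**The numerator is not certain either.** Read as a true alternative, "Baseline values or any prior post-baseline values do not meet the thresholds listed in Appendix 4" lets a subject who is abnormal at baseline, normalises and rises again count as a case. The abnormal-baseline and resolved classes in the same section also include subjects raised at baseline. This stands; p(1 − q) is exact only under the stricter reading, which the protocol's at-risk wording favours.

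**Little depends on it.** The all-subject percentage is a valid quantity, though a different one. No confirmatory test uses these tables. The planned shift tables show baseline status by normal range, PCS and CS cases are listed, and hepatic and renal events have their own searches. This stands and sets the severity.

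**Stronger inferences.** A reader might conclude that every laboratory rate is understated; the rows exempted under step 2 show otherwise. A reader might suspect a bias between arms; randomisation balances q in expectation. A reader might also call the Hy's Law percentage a departure from the protocol; the protocol's laboratory analysis section contains no such rate to depart from.

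**Conclusion.** The point holds for PCS/CS rows that a subject can already meet at baseline, mainly the mild ALT, AST and CK bands. Under the SAP's default denominator, the percentage falls below the protocol's planned incidence by q in relative terms and p × q in absolute terms. At an assumed p of 20% and q of 10% to 30%, that is 2 to 6 points. Both values are assumptions, and the result also rests on the stricter reading of the numerator rule and on applying SAP 6.3.1 as written.

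The documents do not support a claim that all the laboratory incidences are too low, or that the comparison between arms is distorted. What they show is a mismatch between protocol and SAP that section 8 does not declare. Severity: minor. Efficacy is untouched.

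**What to change.** In SAP 6.4.8.2:

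1. For each threshold that carries the baseline exclusion, define the denominator as Safety Population subjects whose baseline value does not meet that threshold and who have at least one post-baseline value. Show n/N on every row. Because the thresholds are bands, a subject in a lower band at baseline stays in the denominator for the higher ones.
2. Reword the condition joining baseline and earlier post-baseline values so that the numerator matches that at-risk set.
3. Report Hy's Law as n/N, with N the subjects who have normal ALT, AST and TBL at baseline. This is for consistency; it does not correct a protocol departure.

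Alternatively, if the all-subject denominator is intended, say so in 6.4.8.2 and list it in SAP section 8 as a change from protocol 10.4.4.2.

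The cost is SAP wording and one denominator variable per row. N will differ between rows, and the printed rates will be slightly higher where q is above zero.

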#### 4.3. Exclusion Criteria

Subjects will be excluded from the study if any of the following exclusion criteria apply prior to randomization:

- 1. Any uncontrolled or serious disease, or any medical or surgical condition, that may either interfere with participation in the clinical study, and/or put the subject at significant risk (according to investigator's [or delegate] judgment) if he/she participates in the clinical study.
- 2. An underlying known disease, or surgical, physical, or medical condition that, in the opinion of the investigator (or delegate) might interfere with interpretation of the clinical study results.
- 3. New York Heart Association (NYHA) class IV heart failure or last known left ventricular ejection fraction <25%.
- 4. Cardiac arrhythmia within 3 months prior to randomization that is not controlled by medication or via ablation.
- 5. Major adverse cardiovascular event within 3 months prior to randomization.
- 6. Uncontrolled severe hypertension: systolic blood pressure >180 mmHg or diastolic blood pressure >110 mmHg prior to randomization despite anti-hypertensive therapy.
- 7. Active liver disease defined as any known current infectious, neoplastic, or metabolic pathology of the liver or unexplained elevations in ALT, aspartate aminotransferase (AST), >3x the ULN, or total bilirubin >2x ULN at screening confirmed by a repeat abnormal measurement at least 1 week apart.
- 8. Severe concomitant noncardiovascular disease that carries the risk of reducing life expectancy to less than 2 years.
- 9. History of malignancy that required surgery (excluding local and wide-local excision), radiation therapy and/or systemic therapy during the three years prior to randomization.
- 10. Females who are pregnant or nursing, or who are of childbearing potential and unwilling to use at least two methods of highly effective contraception (failure rate less than 1% per year) (eg combined oral contraceptives, barrier methods, approved contraceptive implant, long- term injectable contraception, or intrauterine device) for the entire duration of the study. Exemptions from this criterion:
  - a. Women >2 years postmenopausal (defined as 1 year or longer since last menstrual period) AND more than 55 years of age.
  - b. Postmenopausal women (as defined above) and less than 55 years of age with a negative pregnancy test within 24 hours of randomization.
  - c. Women who are surgically sterilized at least 3 months prior to enrollment.

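### The SAP's new-occurrence rule for PCS laboratory values conflicts with the Abnormal baseline class it then applies to ALT, AST and CK

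*SAP*

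**What the plan says.** SAP 6.4.8.2 sets HbA1c apart ("Hemoglobin A1c criteria is explicitly stated in Appendix 4"). For every other parameter, "All other PCS and CS criteria are met when both of the following occur": first, "Post-baseline values meet the thresholds listed in Appendix 4"; second, "Baseline values or any prior post-baseline values do not meet the thresholds listed in Appendix 4". Appendix 4 repeats the pair.

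Appendix 4 gives ALT, AST and CK several bands in multiples of ULN and stars the clinically significant (CS) ones. For ALT and AST the only unstarred band is above 1 and up to 3 times ULN. CK has two unstarred bands: that one, and above 3 and up to 5 times ULN.

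The same SAP section continues: "PCS chemistry laboratory values will also be classified as follows". Three of the five classes can start from an abnormal baseline:

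- Abnormal baseline (non-HbA1c): above 1 and up to 3 times ULN at baseline and again at the final visit.
- Elevated further: in that range at baseline or later, then above 3 times ULN.
- Resolved: in that range at baseline or later, then back below ULN through the final visit.

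Protocol 10.4.4.2 restricts PCS/CS incidence to subjects who had no such value at baseline. SAP Section 8 records that the identification of PCS/CS values was modified, without saying how.

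**The concern.** The definition asks for a baseline outside the band; the class asks for a baseline inside it. If the classes subdivide PCS values, a subject who enters with ALT at twice ULN and stays there belongs in Abnormal baseline by description but is barred by definition.

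Such subjects can be enrolled. Exclusion 7 in Protocol 4.3 removes only unexplained, confirmed ALT or AST above 3 times ULN, and no exclusion criterion sets a CK limit. Many subjects will be on maximally tolerated statins.

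The five-class table is the planned display of how a baseline liver-enzyme or CK elevation evolves. A zero in a baseline-origin cell could be read as no such subjects when it only reflects the rule. Because the rule can be read in several ways, two competent programmers could also produce quite different tables.

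**Working it through.** The SAP gives no figure to reproduce. The question is which class members can also satisfy the PCS rule.

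**Inputs.** Baseline plus the seven post-baseline chemistry visits (Days 90, 150, 270, 330, 450, 510 and 540), and four bands: up to 1, above 1 to 3, above 3 to 5, and above 5 times ULN.

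**Sequences.** All: 4^8 = 65,536. Abnormal baseline fixes the first and last visit in the second band, leaving 4^6 = 4,096. Of these, 2^6 = 64 never exceed 3 times ULN. The counts show only whether a cell can be populated; they are not expected frequencies.

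**Abnormal baseline sequences that can be PCS, out of 4,096:**

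| Reading of the second condition | ALT/AST, unstarred band only | CK, both unstarred bands | ALT, AST or CK, CS bands also counted |
|---|---|---|---|
| Neither/nor, same band | 0 | 3,367 | 4,032 |
| Neither/nor, any band | 0 | 0 | 0 |
| Literal or, same band | 4,095 | 4,095 | 4,095 |

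Where the non-zero counts come from:

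- 3,367 = 4,096 − 3^6 (729 sequences never visit the above 3 to 5 band). Example: CK at 2 times ULN at baseline, 4 times mid-study, 2 times at the end.
- 4,032 = 4,096 − 2^6 (64 never exceed 3 times ULN).
- 4,095 = 4,096 − 1 (the constant sequence). Example admitted: 2 times ULN at baseline, normal at Day 90, 2 times ULN from Day 150 to the end.

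**The 64 sequences never above 3 times ULN.** None is PCS under either neither/nor reading; 63 are under the literal or. The one at a constant 2 times ULN is not PCS under any reading.

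**Other classes, baseline-origin part.** Elevated further: 4^7 − 2^7 = 16,384 − 128 = 16,256 sequences. Resolved: 4^6 = 4,096. For ALT and AST with only the unstarred band counted, 0 of 16,256 and 0 of 4,096 can be PCS under both neither/nor readings. For CK both are 0 under the any-band reading; under the same-band reading with its two unstarred bands they are 14,197 and 3,367.

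**HbA1c.** A rise from 7.0% to 7.6% at the final visit (change 0.6) meets the Appendix 4 criterion and also the HbA1c line of Abnormal baseline, so that part of the class can be populated.

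**The case against.** A reader might infer that Abnormal baseline must always be empty. The documents do not support that:

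- HbA1c is exempt from the two-condition rule.
- CK can enter through its second unstarred band if thresholds are read band by band.
- ALT, AST and CK can all enter, band by band, if starred CS values count as PCS, which the SAP leaves open.
- The SAP literally says or, and that admits nearly every sequence. Protocol 10.4.4.2 favours neither/nor, but SAP Section 8 says PCS/CS identification was changed, so the protocol is not decisive.

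Nor do continuing abnormalities disappear from the report. SAP 6.4.8.2 also plans by-visit summaries and a shift table of baseline against worst post-baseline value, with no new-occurrence restriction. Leaving baseline-abnormal subjects out of PCS incidence is what the protocol intends. Elevated further and Resolved also keep their post-baseline routes.

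A headcount is tempting too, but the documents give no proportion above ULN at baseline. Even an assumed proportion would not measure the empty class, which also requires the value to be in range at the final visit.

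All of this stands, and it limits the point without removing it. No reading admits the constant mild elevation. The other displays are only partial substitutes: by-visit summaries are group-level, and a high-to-high shift based on the worst value does not separate stable, resolved and further-elevated subjects.

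**Conclusion.** Wrong as written, of low severity (nice to have). The conflict between the PCS definition and the non-HbA1c classes is in the text. Under neither/nor, ALT, AST or CK values that stay above 1 and up to 3 times ULN from baseline can never enter Abnormal baseline. For ALT and AST with only the unstarred band counted, that whole class and the baseline-origin parts of Elevated further and Resolved are empty. For CK the result depends on whether threshold means the same band or any band. HbA1c is unaffected.

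This rests on the neither/nor reading, except for the constant elevation, which is shut out under every reading tested. The effect is confined to one safety table and its cell counts; no efficacy result is involved, and the number of subjects affected cannot be derived from the documents.

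**What to change.** In SAP 6.4.8.2 and Appendix 4:

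1. Define the non-HbA1c five-class table on all subjects with any ALT, AST or CK value above ULN at baseline or later, independent of the new-occurrence rule. Leave the HbA1c lines as they are.
2. Keep the new-occurrence rule for PCS/CS incidence only, worded so that neither baseline nor any earlier post-baseline value meets the threshold.
3. State whether threshold means the same band or any Appendix 4 band for that parameter.
4. State whether CS values also count as PCS.

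On the wider base, a constant mild elevation would satisfy both Abnormal baseline and Persistently elevated, so say whether a subject may appear in more than one class.

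The cost is SAP wording and a changed denominator in one table. No extra data are needed.
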